**ID: COPD-141316051**

**NCT02251496**

## **COPD: Oral Nutrition Supplements vs. Energy- and Protein Dense in Between Meal Snacks.**

**[name]**

**12/23/2020**

## METHODS

### Study design and participants

This study was a randomised trial and registered at clinicaltrials.gov on September 25, 2014. ClinicalTrials.gov identifier: [NCT02251496](https://clinicaltrials.gov/ct2/show/NCT02251496). The study was approved by the National Bioethics Committee (VSN14-066-S1), Chief medical officer Landspitali (LSH 68-14) and Data Protection Authority (2014/908) and conducted in line with the Declaration of Helsinki. The study follows the CONSORT 2010 statement: extension to randomised pilot and feasibility trials. (Eldridge et al., 2016)

Patients with a clinical diagnoses of COPD who had been recently admitted to the Department of Respiratory Medicine at Landspitali University Hospital were screened for possible nutritional risk (score  $\geq 4$ ) by a trained researcher using a validated nutritional screening tool. (Ingadottir et al.; Thorsdottir, Gunnarsdottir, & Eriksen, 2001) The Icelandic Simple Screening (ISS) used is recommended by the clinical guidelines for hospital nutrition at Landspitali (Friðriksdóttir, 2011) and has been validated against a full nutritional assessment in COPD patients (Thorsdottir et al., 2001) and predicts mortality in COPD patients. (Ingadottir et al.) ISS gathers information on BMI, unintentional weight loss, age, co-morbidities, recent hospitalisation and a range of symptoms that impact nutritional intake during the last weeks or months (vomiting, diarrhoea, loss of appetite or nausea, difficulties in chewing or swallowing).

All eligible patients who were able to eat orally, and had an anticipated length of hospitalisation of  $>3$  days were invited to participate in the study. The most common reason for admission was acute exacerbation of COPD. Written informed consent was obtained from all participants.

Patients diagnosed with cancer, dysphagia, food allergy or intolerance and anatomical obstructions preventing oral food intake were excluded. Patients not able to sign informed consent due to cognitive issues were also excluded.

Socio-demographic data (age, gender and smoking status) were collected from electronic medical records SAGA (TM software 3.1.39.9).

### Randomisation and masking

Eligible patients were randomly assigned in a 1:1 ratio to either an ONS group (ONS) or snacks group. Random sequence generation was performed using randomisation codes produced by Microsoft Excel for Windows 2007. Randomisation, allocation of patients to groups, nutritional intervention and outcome assessments were performed by one researcher

([name]). Due to the nature of the intervention it was not possible to perform a blinded study. Randomisation took place after screening for nutritional risk and prior to baseline assessment.

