### **Procedures**

This study was originally designed as a randomized trial to investigate the effects of snacks on body weight and QoL in COPD patients compared to ONS with a planned enrolment of 200 subjects (ClinicalTrials.gov, number [NCT02251496](#)). Despite screening 492 subjects only 76 subjects were eligible indicating that recruitment is challenging in this population and clinical setting. Recruitment rates were lower than expected which led to a change in the study protocol to a randomised feasibility trial as funding was limited to three years. One reason for low recruitment rates might be over strict inclusion criteria. More details on study recruitment are provided in the results.

Nutritional screening was undertaken on admission using the validated screening tool as recommended for use at the Landspitali. (Friðriksdóttir, 2011; Ingadottir et al.; Thorsdottir et al., 2001) A total score of  $\geq 4$  is considered ‘at nutritional risk’.

After providing informed consent, subjects were randomly allocated to one of two groups. Subjects in group 1 were provided with ONS and subjects in group 2 were provided with snacks (Table 1). The intervention started in hospital and was continued for 12 months after discharge from the hospital.

**Table 1** Nutritional content of each intervention products.

Oral nutritional supplement drinks			
Product	Portion size	Energy (kcal)	Protein (g)
Nutridrink compact (Nutricia) e.g. vanilla, banana, strawberry and chocolate	125 ml	300	12
Nutridrink compact fiber (Nutricia) -vanilla, strawberry and mokka	125 ml	300	12
Nutridrink (Nutricia) -vanilla, strawberry, banana, and chocolate	200 ml	300	12
Nutridrink juice style (Nutricia) e.g. blackcurrant, apple and orange	200 ml	300	8
Nutridrink creme (Nutricia) -forest fruit and chocolate	125 g	200	12
Mean		280	11
In-between meals snack			
Product	Portion size	Energy (kcal)	Protein (g)
Blueberry skyr with cream (MS Dairies)	Skyr 140 g Cream 20 ml	254	17
Two mini skyr with cream (MS Dairies) -vanilla, strawberry and banana	Skyr 167 g Cream 20 ml	274	16
Rye bread (Myllan) with liver paté (Ora) and butter (MS Dairies)	Rye bread 55 g Liver paté 40 g Butter 10 g	313	7
Pan bread (Myllan) with ham- and egg salat (Sómi)	Pan bread 47 g Salat 55 g	262	8
Oat biscuits (Frón) with butter, cheese and glass of milk (MS Dairies)	Oat biscuit 20 g Butter 10 g Cheese 20 g Milk 150 ml	342	12

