Nutbar (Himneskt) with milk (MS Dairies)	Nutbar 40 g Milk 150 ml	302	10
Cheesecake (MS Dairies) -raspberry and chocolate	100 g	322	6
Mean		286	11

Subjects in group 1 were offered a variety of flavours and pack sizes of ONS free of charge. As the hospital had a contract with Nutricia (Icepharma, Iceland) that was the brand used. Subjects in group 2 were provided with snacks free of charge, based on common Icelandic food products, e.g., Icelandic skyr which is a high protein milk product similar to yogurt. Patients in both groups were encouraged to consume two or more ONS or Snacks daily providing approximately 600 kcal/day and approximately 22 g protein/day in addition to regular food depending on which group they were in.(Collins, Stratton, & Elia, 2012; Ferreira, Brooks, White, & Goldstein, 2012)

The selected ONS were delivered to the patient's home or picked up at the wholesaler and the food packages were delivered to patient's home or collected from the hospital, according to patient preference. It was assumed that each delivery of ONS and Snacks would last for one month and two to three weeks, respectively. A leaflet designed for this study was provided with pictures of different ONS or each snack and written advice regarding their use such as suggestions on timing of intake, choosing a lower volume (125 ml each) when appetite was poor (ONS) and choice of different meals (Snacks). For some items, patients had to portion the snacks themselves, e.g., a whole cheesecake, because the minimal available pack size was more than one portion.

Verbal advice on the use of each intervention was also given to both groups, e.g., ONS should be used from the fridge and snacks with less expiry date should be used first.

All patients could phone the study investigator if they needed more ONS or snacks and every month each patient received a call to ascertain the quantity remaining. If patients were admitted to hospital during the study period they received ONS or snacks according to randomisation during their hospital stay.

During every follow-up appointment and during any hospital readmissions similar time was spent with each group.

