## **Outcomes**

Outcomes related to feasibility were percentage of eligible subjects that accepted participation (recruitment), percentage of included subjects that finished the 12 months intervention period (retention), the feasibility of undertaking functional assessment and use of ONS/snacks assessed by 24 hour recalls (compliance).

The primary outcome was efficacy of the interventions assessed as weight change from baseline to one year from admission to the hospital. Assessment of body composition i.e.

fat mass, fat free mass and muscle mass was conducted using a portable, multi- frequency (20kHz, 100kHz) bioelectrical impedance analysis (BIA) device (InBody230 Co., Ltd. Korea). The method has previously been validated in stable COPD patients. (Schols, Broekhuizen, Weling-Scheepers, & Wouters, 2005)

The secondary outcome measures were QoL measured using the St George's Respiratory Questionnaire (SGRQ). This validated questionnaire is based on 76 items used to calculate three component scores: symptoms, activity and impact, and a total score. A score of 100 represents worst possible health status and a score of 0 represents best possible health status. (Jones, Quirk, Baveystock, & Littlejohns, 1992) A change of 4 points in the SGRQ total score is considered the minimum clinically relevant difference. (Jones, 2002)

Other outcomes measures included were forced expiratory volume in one second (FEV1), forced vital capacity (FVC) measured by spirometry (Jaeger MS-PFT®, Care Fusion, San Diego, USA), (Vogelmeier et al., 2017) functional performance using several tests validated in COPD patients were included: six-minute walk distance (6MWD), (Singh et al., 2014) timed up and go (TUG), (Mesquita et al., 2016) 30 second chair stand (Kato et al., 2014) and hand-grip strength (HGS) (Puhan, Siebeling, Zoller, Muggensturm, & ter Riet, 2013) measured by a handheld dynamometer (Jamar® Sammons Preston Rolyan, Boilingbrook, IL, USA) and energy- and protein intake during hospital stay and at home (two and four weeks after discharge).

Total energy- and protein intake during hospital stay was estimated using a validated plate diagram sheet (Bjornsdottir et al., 2013; Vilhjalmsdottir, Hinrikssdottir, Pordardottir, Porsdottir, & Gunnarsdottir, 2013) for three days, starting on the first day of participation in the study and after the intervention had started.

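### Randomisation came before baseline assessment in an unblinded, single-researcher trial: a minor, avoidable risk of bias, near nil for measured weight and possible for SGRQ

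*Protocol*

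**What the plan says.** The Protocol, Randomisation and masking, gives the order outright: "Randomisation took place after screening for nutritional risk and prior to baseline assessment". The same section says "Due to the nature of the intervention it was not possible to perform a blinded study" and "Randomisation, allocation of patients to groups, nutritional intervention and outcome assessments were performed by one researcher".

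Procedures places consent first: "After providing informed consent, subjects were randomly allocated to one of two groups". No reason is given for leaving baseline until after allocation.

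Outcomes defines the primary outcome as "weight change from baseline to one year from admission to the hospital". The Statistical analysis sections of the Protocol and the SAP describe an intention-to-treat analysis limited to patients with a baseline and at least one later measure. They name a repeated measures ANCOVA but no covariates. Outcomes refers to an Appendix 1 for assessment details; it is not among the documents supplied.

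**The concern.** A baseline measured before allocation cannot depend on arm. One measured afterwards, by the person who made the allocation and will deliver the product, can. There are two routes.

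- **Measurement.** The recorded baseline may shift with arm, and it then enters every change from baseline. Weight leaves little room for this. SGRQ is reported by the patient, and walking distance, timed up and go, chair stand and grip strength depend on effort, so they leave more.
- **Selection.** A patient randomised but lost before baseline cannot enter the analysis set. If such losses differ by arm, the comparison is no longer fully randomised, and this route also reaches weight.

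Because consent preceded allocation, both routes could have been closed by taking the same measurements earlier.

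**Working it through.** **Inputs from the documents.** The order of events, as above; nominal level 0.05 (sidedness not stated, two-sided assumed); Table 1 mean energy per portion of 280 kcal for ONS and 286 kcal for snacks; the common target, "Patients in both groups were encouraged to consume two or more ONS or Snacks daily providing approximately 600 kcal/day"; the SGRQ threshold, "A change of 4 points in the SGRQ total score is considered the minimum clinically relevant difference"; and the only head count near the analysed size, "Despite screening 492 subjects only 76 subjects were eligible".

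**Assumptions.** The documents give no SD, no number per arm and no interval from randomisation to baseline. I use 38 per arm (an equal split of 76) and 20 per arm as illustrations. There is no figure in the plan to reproduce on this point.

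**Formulae.** Let s be the arm difference in recorded baseline caused by the order, and f the arm difference at follow-up caused by unblinded assessment.

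- Bias of a change score: f − s. Bias after baseline adjustment: f − slope × s.
- SE of the change-score difference: SD × √(2/n). With adjustment, taking slope = r and equal variances, multiply by √((1+r)/2).
- Type I error with bias b: P(Z > 1.96 − |b|/SE) + P(Z < −1.96 − |b|/SE).

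**Weight.** Assume 7700 kcal per kg and a lag of 1 to 3 days.

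- Two portions a day at the Table 1 means differ by 2 × (286 − 280) = 12 kcal/day, that is 12/7700 = 0.002 kg to 36/7700 = 0.005 kg.
- In the extreme case one arm takes the full 600 kcal/day and the other none: 600/7700 = 0.08 kg to 1800/7700 = 0.23 kg.
- At 0.23 kg, SD of change 3, 5 or 7 kg: with 38 per arm (SE 0.688, 1.147, 1.606) type I error is 6.3%, 5.5%, 5.2%; with 20 per arm (SE 0.949, 1.581, 2.214) it is 5.7%, 5.3%, 5.1%. At 0.08 kg every case lies between 5.0% and 5.2%.

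**SGRQ.** Assume s = 2 points (half the 4-point threshold) and f = 0.

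| SD of change | SE, 38 per arm | Unadjusted, b = 2 | Adjusted, slope 0.5 (b = 1) to 0.8 (b = 1.6) |
|---|---|---|---|
| 10 | 2.294 | 14.1% | 8.0–11.4% |
| 15 | 3.441 | 9.0% | 6.3–7.8% |
| 20 | 4.588 | 7.2% | 5.7–6.6% |

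At SD 10, for example, the adjusted SE is 2.294 × √0.75 = 1.987 for slope 0.5 and 2.294 × √0.9 = 2.176 for slope 0.8. With 20 per arm the unadjusted values fall to 9.7%, 7.1% and 6.2%. A 1-point shift with 38 per arm gives 7.2%, 6.0% and 5.5%. Since no covariates are named, the documents do not settle which column applies.

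**With a follow-up shift as well** (change score, s = 2, 38 per arm, SD 10/15/20). If f = +2, the errors cancel under the present order (5%), and re-ordering leaves |b| = 2: 14%/9%/7.2%. If f = −2, the present order gives |b| = 4: 41%/21%/14%, and re-ordering lowers this to 14%/9%/7.2%.

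**Selection.** If a net 5% of one arm were lost before baseline and differed by 3 kg in weight change, the bias would be 0.05 × 3 = 0.15 kg. With 10% and 5 kg it would be 0.5 kg, a type I error of 6.5–8.5% at 38 per arm and SD 6 to 4 kg. The documents report no such loss.

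**The case against.** The opposing case is strong on size.

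- The primary outcome is barely touched. The upper end for weight needs one arm to take the full target and the other nothing, although both arms had the same target.
- For SGRQ, only the 4-point threshold comes from the documents. The shift, SDs, slopes and arm sizes are chosen. Both arms receive an active product, a shift common to both cancels, and no mechanism is evident for ONS and snack patients to answer differently at baseline. The Protocol's own reference describes the questionnaire as self-completed, which limits the researcher's influence, and the documents do not say when patients learned their arm.
- The effort-dependent tests are not quantified here.
- Re-ordering leaves unblinded follow-up in place and could even raise net bias if the two errors would have cancelled.
- Most patients were admitted with an acute exacerbation, and whether functional testing was feasible was itself an outcome. Insisting on those tests before allocation could cost recruitment.

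All of this stands, and it is why the point is minor. It does not remove the point. Appendix 1 may give the timing, but it cannot reverse the order that the Protocol states. Chance cancellation is not a safeguard, whereas a baseline fixed before allocation is.

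**Conclusion.** The order of randomisation and baseline is an avoidable risk of bias of unknown direction. Severity: minor. Measurement bias in weight is near nil, at 5.0–6.3% under extreme assumptions. For SGRQ it is possible: about 14%/9%/7% unadjusted and about 8–11%/6–8%/6–7% adjusted, for a 2-point shift, 38 per arm and an SD of change of 10/15/20, all of them assumed. An effect on the effort-dependent tests is plausible but not quantified.

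A reader might infer more than the documents support:

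- **That bias occurred, or that patients were dropped for want of a baseline.** Neither is documented.
- **That baseline was taken after the first product.** Outcomes says the in-hospital intake record began once the intervention had started, but that is an intake measure. It does not date baseline weight or SGRQ.
- **That the weight result is undermined.** The figures above do not support this for measurement, and the selection route has no reported losses behind it.
- **That re-ordering guarantees a smaller net bias.** It sets only the s term to zero.

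**What to change.** **In this design and any definitive trial built on it:** after consent and before the allocation is opened, take baseline weight, body composition and SGRQ. Attempt the functional tests in the same window, but do not make completing them a condition of randomisation.

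**For the data already collected:** report by arm the number randomised without a baseline. If a measured screening weight from before randomisation was kept, use it as baseline in a sensitivity analysis. Screening collected BMI, but the documents do not say whether the weight behind it was measured or reported.

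**Cost:** no measurement is added. Some baselines will be taken on patients who are then not randomised, and allocation opens later by a time that cannot be estimated, because the documents give no in-hospital schedule. For the existing data the cost is one count by arm and one conditional analysis.

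**What it secures:** baseline values taken in that window, and exclusions for lacking them, can no longer depend on arm. A functional test first completed after allocation stays exposed, and unblinded follow-up needs its own remedy.

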### **Procedures**

This study was originally designed as a randomized trial to investigate the effects of snacks on body weight and QoL in COPD patients compared to ONS with a planned enrolment of 200 subjects (ClinicalTrials.gov, number [NCT02251496](#)). Despite screening 492 subjects only 76 subjects were eligible indicating that recruitment is challenging in this population and clinical setting. Recruitment rates were lower than expected which led to a change in the study protocol to a randomised feasibility trial as funding was limited to three years. One reason for low recruitment rates might be over strict inclusion criteria. More details on study recruitment are provided in the results.

Nutritional screening was undertaken on admission using the validated screening tool as recommended for use at the Landspitali. (Friðriksdóttir, 2011; Ingadottir et al.; Thorsdottir et al., 2001) A total score of  $\geq 4$  is considered ‘at nutritional risk’.

After providing informed consent, subjects were randomly allocated to one of two groups. Subjects in group 1 were provided with ONS and subjects in group 2 were provided with snacks (Table 1). The intervention started in hospital and was continued for 12 months after discharge from the hospital.

**Table 1** Nutritional content of each intervention products.

Oral nutritional supplement drinks			
Product	Portion size	Energy (kcal)	Protein (g)
Nutridrink compact (Nutricia) e.g. vanilla, banana, strawberry and chocolate	125 ml	300	12
Nutridrink compact fiber (Nutricia) -vanilla, strawberry and mokka	125 ml	300	12
Nutridrink (Nutricia) -vanilla, strawberry, banana, and chocolate	200 ml	300	12
Nutridrink juice style (Nutricia) e.g. blackcurrant, apple and orange	200 ml	300	8
Nutridrink creme (Nutricia) -forest fruit and chocolate	125 g	200	12
Mean		280	11
In-between meals snack			
Product	Portion size	Energy (kcal)	Protein (g)
Blueberry skyr with cream (MS Dairies)	Skyr 140 g Cream 20 ml	254	17
Two mini skyr with cream (MS Dairies) -vanilla, strawberry and banana	Skyr 167 g Cream 20 ml	274	16
Rye bread (Myllan) with liver paté (Ora) and butter (MS Dairies)	Rye bread 55 g Liver paté 40 g Butter 10 g	313	7
Pan bread (Myllan) with ham- and egg salat (Sómi)	Pan bread 47 g Salat 55 g	262	8
Oat biscuits (Frón) with butter, cheese and glass of milk (MS Dairies)	Oat biscuit 20 g Butter 10 g Cheese 20 g Milk 150 ml	342	12
Nutbar (Himneskt) with milk (MS Dairies)	Nutbar 40 g Milk 150 ml	302	10
Cheesecake (MS Dairies) -raspberry and chocolate	100 g	322	6
Mean		286	11

Subjects in group 1 were offered a variety of flavours and pack sizes of ONS free of charge. As the hospital had a contract with Nutricia (Icepharma, Iceland) that was the brand used. Subjects in group 2 were provided with snacks free of charge, based on common Icelandic food products, e.g., Icelandic skyr which is a high protein milk product similar to yogurt. Patients in both groups were encouraged to consume two or more ONS or Snacks daily providing approximately 600 kcal/day and approximately 22 g protein/day in addition to regular food depending on which group they were in.(Collins, Stratton, & Elia, 2012; Ferreira, Brooks, White, & Goldstein, 2012)

The selected ONS were delivered to the patient's home or picked up at the wholesaler and the food packages were delivered to patient's home or collected from the hospital, according to patient preference. It was assumed that each delivery of ONS and Snacks would last for one month and two to three weeks, respectively. A leaflet designed for this study was provided with pictures of different ONS or each snack and written advice regarding their use such as suggestions on timing of intake, choosing a lower volume (125 ml each) when appetite was poor (ONS) and choice of different meals (Snacks). For some items, patients had to portion the snacks themselves, e.g., a whole cheesecake, because the minimal available pack size was more than one portion.

Verbal advice on the use of each intervention was also given to both groups, e.g., ONS should be used from the fridge and snacks with less expiry date should be used first.

All patients could phone the study investigator if they needed more ONS or snacks and every month each patient received a call to ascertain the quantity remaining. If patients were admitted to hospital during the study period they received ONS or snacks according to randomisation during their hospital stay.

During every follow-up appointment and during any hospital readmissions similar time was spent with each group.

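### Does the snack energy mean in Table 1 (286 kcal, where its seven rows average 296) undermine the energy match between the arms?

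*Protocol*

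**What the plan says.** Protocol, Procedures, Table 1 ("Nutritional content of each intervention products") lists five ONS products and seven snacks, each with portion size, energy and protein, and closes each block with a mean. The ONS means are 280 kcal and 11 g; the snack means are 286 kcal and 11 g. Typical snack rows read "Skyr 140 g Cream 20 ml 254 17" and "Oat biscuit 20 g Butter 10 g Cheese 20 g Milk 150 ml 342 12", with energy and then protein as the last two figures. The last snack row, "Cheesecake (MS Dairies) -raspberry and chocolate", is listed at 322 kcal and 6 g.

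The paragraph after the table sets a single target for both arms: patients were "encouraged to consume two or more ONS or Snacks daily providing approximately 600 kcal/day and approximately 22 g protein/day".

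Under Outcomes, the primary outcome is weight change from baseline to one year. The same section describes energy and protein intake measured by a three-day plate diagram in hospital and by 24-hour recall at two and four weeks after discharge, with the recalls analysed in a nutrient database program. It refers to an appendix for the full assessments. Neither the Protocol's Statistical analysis section nor the SAP mentions Table 1.

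**The concern.** The trial compares two ways of delivering extra energy and judges them on body weight. A reader therefore looks to Table 1 to see whether the arms offer about the same energy per portion. The printed means, 280 and 286, suggest that they do. If the snack mean is really 296, the nominal gap is 2.6 times what the table shows (15.6 / 6), with snacks the higher.

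It would then be harder to say whether a weight difference in favour of snacks came from the form of the supplement or from extra energy. If instead one of the rows is wrong, that product's listed energy is wrong. Only one of the four means fails to reproduce, so a rounding or averaging convention does not explain it.

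**Working it through.** **Inputs** (Protocol, Table 1)

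- ONS energy: 300, 300, 300, 300, 200 kcal. ONS protein: 12, 12, 12, 8, 12 g.
- Snack energy: 254, 274, 313, 262, 342, 302, 322 kcal. Snack protein: 17, 16, 7, 8, 12, 10, 6 g.

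**Step 1: reproduce the printed means as plain row averages**

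| Mean | Calculation | Result | Printed |
|---|---|---|---|
| ONS energy | 1400 / 5 | 280 | 280 |
| ONS protein | 56 / 5 | 11.2 | 11 |
| Snack protein | 76 / 7 | 10.9 | 11 |
| Snack energy | 2069 / 7 | 295.6 | 286 |

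Three of four reproduce. A snack mean of 286 would need a sum of 7 × 286 = 2002, which is 2069 − 2002 = 67 kcal less than the rows give.

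**Step 2: look for another route to 286**

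- Median 302; geometric mean 294.0; harmonic mean 292.4; midrange 298.
- Weighted by listed flavours: 293.9 (mini skyr three times, cheesecake twice) or 290.8 (mini skyr three times only).
- Weighted by portion size, counting ml as g: 296.4.
- Dropping any one row: 287.8 to 302.5.
- Dropping any two rows: the nearest values are (2069 − 342 − 302) / 5 = 285.0 and (2069 − 313 − 322) / 5 = 286.8.

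None rounds to 286. The printed 286 differs from the rounded row average, 296, in one digit. That suggests a slip in the mean but does not prove it.

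**Step 3: size of the nominal gap, snacks minus ONS**

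| | From the rows | As printed | Due to the discrepancy |
|---|---|---|---|
| Per portion | 295.6 − 280 = 15.6 kcal (5.6% of 280) | 286 − 280 = 6 kcal (2.1%) | 9.6 kcal |
| Two portions a day | 591 − 560 = 31 kcal | 572 − 560 = 12 kcal | 19 kcal |
| 365 days at two portions | 11,367 kcal | 4,380 kcal | 6,987 kcal |

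The yearly figures assume full use every day and equal choice of all products.

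**Step 4: compare with the variation the design allows**

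- The rows span 200 to 300 kcal for ONS (100 kcal) and 254 to 342 kcal for snacks (88 kcal). Both spans are about ten times the 9.6 kcal discrepancy.
- Four of the five ONS rows are 300 kcal. A patient who takes none of the 200 kcal product gets 2 × 300 = 600 kcal from two portions, against 591 from two average snacks. The gap is then 9 kcal/day in the other direction.
- One extra portion, which the wording on portion number permits, adds roughly 280 to 296 kcal.

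**Step 5: compare with the stated daily target**

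Two snack portions give 572 kcal on the printed mean and 591 on the rows. The row-based figure is the closer of the two to the approximate 600 in the text. The ONS figure, 560, is unaffected.

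**Step 6: trace where 286 is used**

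Nothing in the Protocol's Statistical analysis section or the SAP draws on it: not the significance level, the power statements, the analysis set, the carrying forward of last observations or the repeated measures ANCOVA. Neither document says that intake was computed from the table mean.

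**The case for a change.** The strongest case for acting is that the error is certain on the printed figures, sits in the table that defines the interventions, and makes the arms look more alike than the rows do, in a trial whose primary outcome responds to energy. The intake measurements described in the text stop at four weeks after discharge while the intervention runs for 12 months, so for most of the year the nominal content is the main stated basis for the energy offered. Checking the table costs almost nothing.

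The inconsistency stands: the rows and the mean cannot both be right, and the documents do not show which is wrong. The limited period of measured intake also stands, but a corrected mean would not extend it. An unweighted average over a product list does not measure what patients ate at any time, because they chose among products and could take more than two portions.

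The inference that the arms were mismatched in energy does not stand. It needs equal choice of every product, and a plausible choice of ONS reverses the sign. The fear that a faulty row would carry into the intake results also lacks support, since neither document says that the table's values feed that analysis. Finally, the randomised comparison is between two supplement strategies as offered. A small difference in nominal energy is part of that contrast and does not bias its estimate; it affects only how a weight difference would be explained.

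**Conclusion.** The concern is right on the arithmetic but leads to no change in the plan. Table 1 is internally inconsistent: 2069 / 7 = 295.6 kcal against a printed 286. If the rows are right, the nominal unweighted gap is about 16 kcal per portion (31 kcal/day at two portions) and not 6 (12 kcal/day). The part due to the discrepancy is 9.6 kcal per portion, or 19 kcal/day, and even that assumes equal choice of products and exactly two portions taken every day.

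This is a clerical slip in a descriptive table. The rows and the mean should be reconciled against source when the table is next reproduced. Whichever figure proves wrong, no endpoint, sample size, analysis or patient instruction in the documents depends on the mean, the text claims only approximate energy for either arm, and the table cannot show what either arm consumed. A fuller revision, such as redescribing how the arms are matched or changing the intake analysis, would gain nothing.
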